1 BACKGROUND AND RATIONALE

Hormone receptor (HR) expression is a common feature of gynecological cancers similar to breast cancer. Among the most common gynecological cancers, 60%- 87% of endometrial and 20%-98% of ovarian cancers are ER+ and/or PR+ depending on the specific subtype (2, 17-23). The recommended treatment for patients with HR+ cancers includes endocrine therapy, alone or combination with chemotherapy or targeted therapy (24-26). However, resistance develops, and disease progression eventually happens (27).

The PI3K/AKT/mTOR signaling pathway is one of the most frequently dysregulated pathways in human cancer (28-33). PI3K/AKT/mTOR pathway regulates critical cellular activities such as proliferation, metabolism, and motility that promote the growth and survival of cancer cells (34). The PI3K/AKT/mTOR pathway can be aberrantly activated by multiple factors, including diverse oncogenic genomic alterations in *PIK3CA*, *PIK3R1*, *PTEN*, *AKT*, *TSC1*, *TSC2*, *LKB1*, *mTOR*, and other critical genes (5, 35-44). *PTEN* negatively regulates PI3K pathway by converting phosphatidyl-inositol-3,4,5-trisphosphate (PIP3) to phosphatidyl-inositol-4-5-bisphosphate (PIP2) (45, 46). PI3K β isoform is the driver of PTEN-null cancers (47). Pan-Class I PI3K or PI3K β -specific inhibitors can be used to target PTEN-deficient tumors. Loss of *PTEN* and increased PI3K signaling have been implicated in resistance to endocrine therapies in ER+ breast cancer, indicating that alterations in PI3K/AKT/mTOR pathway might also contribute to resistance in other HR+ gynecological cancers to endocrine therapies (3, 48-51).

Endometrial cancer is the leading gynecological cancer in the United States and is characterized by an activated PI3K pathway as a result of *PTEN* inactivating and/or *PIK3CA*-activating and *PIK3R1*-inactivating alterations (52). 63%, 39%, and 33% of endometrial cancers harbor inactivating *PTEN* alterations according to The Cancer Genome Atlas (TCGA) studies, Catalogue of Somatic Mutations in Cancer (COSMIC) database, and a study from our group, respectively. *PIK3CA* and *PIK3R1* mutations were identified in 25-52% and 22-28% of endometrial cancers, respectively (28, 53, 54). Interestingly, *PIK3CA* and *PTEN* are frequently mutated simultaneously in endometrial cancers (28, 52).

Ovarian cancer is the most lethal gynecological malignancy in the United States and other developed countries. According to the TCGA study, *PIK3CA* is altered in 21% of ovarian cancers. More than 90% of the *PIK3CA* alterations in ovarian cancers are gene amplifications. Alterations in *PTEN* and *PIK3R1* are also identified in ovarian cancers at lower rates (6% and 3%, respectively) (54).

Investigations of the therapeutic targeting of the PI3K/AKT/mTOR pathway have resulted in the development of several distinct classes of pathway inhibitors, including PI3K and AKT inhibitors, as well as allosteric mTOR and catalytic mTOR kinase inhibitors (28). Despite the significant effort invested in the preclinical and clinical development of compounds targeting the PI3K/AKT/mTOR pathway, only a few have been approved for clinical use. There are several possible reasons for this lack of headway (55-59). Most inhibitors of the oncogenically activated PI3K/AKT/mTOR pathway have low ORRs when used as monotherapy (55, 56). The relatively modest activity is

Proprietary Information of MD Anderson

Protocol 2020-1241

19 October 2022

often explained by negative feedback loops that result in pathway reactivation (6, 60-63). Early clinical data suggest that combinations of inhibitors targeting the PI3K/AKT/mTOR pathway are more effective than inhibitor monotherapies (5, 7).

[figure not shown]
Supporting the concept, pan-PI3Ki buparlisib in combination with fulvestrant doubled the median PFS in patients with *PIK3CA*-mutant versus wild-type advanced breast cancer as demonstrated in 2 phase 3 trials (64, 65). Another Phase 1 trial tested the mTOR inhibitor everolimus in combination with aromatase inhibitor anastrozole in advanced gynecological and breast malignancies. Everolimus- anastrozole combination achieved SD/PR/CR in 24% of patients (n=50) (15) The clinical benefit of the PI3K pathway inhibitors and endocrine therapy combination can be extended to other HR+ solid cancers harboring alterations that activate the PI3K pathway.

Proprietary Information of MD Anderson

Protocol 2020-1241

19 October 2022

Proprietary Information of MD Anderson

Protocol 2020-1241

19 October 2022

[figure not shown]
Proprietary Information of MD Anderson

Protocol 2020-1241

19 October 2022

Class I PI3K subfamily is comprised of four isoforms; PI3K α , PI3K β , PI3K γ , and PI3K δ . All of these isoforms have a catalytic P110 subunit (66, 67). PI3K α signaling is frequently implicated in a variety of cancer types. Tumors harboring alterations activating *PIK3CA* or de-activating *PTEN* are sensitive to PI3K α inhibitors. Specific inhibition of PI3K δ demonstrated remarkable therapeutic efficacy in certain human leukemias and lymphomas (68). PI3K δ inhibition in B-cell malignancies prevents tumor cells from responding to supportive stimuli from the microenvironment (69). Mice experiments have shown that PI3K δ inhibition can protect against a variety of cancers, including solid tumors, by breaking the regulatory CD4+ T-cell (Treg)-mediated immune tolerance to activate cytotoxic T- cell response (70).

[figure not shown]
Copanlisib is approved for the treatment of adult patients with relapsed follicular lymphoma who have received at least two prior systemic therapies (FDA, 2017).

Proprietary Information of MD Anderson

Protocol 2020-1241

[figure not shown]
19 October 2022

Proprietary Information of MD Anderson

Protocol 2020-1241

[figure not shown]
19 October 2022

Proprietary Information of MD Anderson

Protocol 2020-1241

19 October 2022

1.2 Fulvestrant

Fulvestrant (Faslodex®) is a competitive ER antagonist that causes degradation of ER upon binding. Fulvestrant significantly down-regulates ER protein and also PR expression consistent with a lack of intrinsic estrogen agonist effects. It is approved for use in the following indications:

- HR+, human epidermal growth factor receptor 2-negative (HER2-) advanced breast cancer in postmenopausal women not previously treated with endocrine therapy.
- HR+ advanced breast cancer in postmenopausal women with disease progression following endocrine therapy.
- HR+, HER2- advanced or metastatic breast cancer in postmenopausal women in combination with ribociclib, as initial endocrine-based therapy or following disease progression on endocrine therapy.
- HR+, HER2- advanced or metastatic breast cancer in combination with palbociclib or abemaciclib in women with disease progression after endocrine therapy.

For more information, refer to the prescribing information.

1.2.1 Safety

The most common, clinically significant adverse reactions occurring in ≥5% of patients receiving Fulvestrant 500 mg were: injection site pain, nausea, bone pain, arthralgia, headache, back pain, fatigue, pain in extremity, hot flash, vomiting, anorexia, asthenia, musculoskeletal pain, cough, dyspnea, and constipation.

Proprietary Information of MD Anderson

Protocol 2020-1241

19 October 2022

Increased hepatic enzymes (ALT, AST, ALP) occurred in >15% of Fulvestrant patients and were not dose-dependent.

There may be overlapping toxicity when combining copanlisib with fulvestrant, based on current clinical experience: gastrointestinal disorders (e.g., nausea), asthenia, and rash have been observed with both copanlisib and fulvestrant.

Increased exposure to fulvestrant is observed in the case of hepatic impairment. Therefore, caution is required when administering the combination of fulvestrant and copanlisib to patients with impaired liver function.

1.3 RATIONALE

1.3.1 Study Rationale and Purpose

The purpose of this study is to evaluate the efficacy and safety of copanlisib in combination with fulvestrant in advanced HR+ solid tumors harboring alterations that activate the PI3K pathway. Copanlisib is a potent pan-PI3Ki approved by the FDA for the treatment of patients with relapsed follicular lymphoma. Fulvestrant is a SERD and is FDA-approved to treat HR+ metastatic breast cancer in addition to other cancers.

Estrogen and/or progesterone receptors are commonly expressed in the ovarian, endometrial, salivary gland, and other cancers (2). Furthermore, we and others found that *PIK3CA-activating*, *PTEN-inactivating* and *PIK3R1-inactivating* mutations frequently occur in these HR-expressing cancers (3-8, 54). Functional inactivation of PTEN by mutations, loss of copy number and epigenetic silencing leads to aberrant activation of PI3K/AKT/mTOR pathway, increasing growth, invasion and metastasis of a diverse set of tumors including breast, endometrial, prostate, renal cell, hepatocellular, glioblastoma and colorectal cancers (75-77).

Endometrial cancer is the leading gynecological cancer in the United States and is characterized by an activated PI3K pathway as a result of *PTEN-inactivating* and/or *PIK3CA-activating* and *PIK3R1-inactivating* alterations (52). 63%, 39%, and 33% of endometrial cancers harbor inactivating *PTEN* alterations according to The Cancer Genome Atlas (TCGA) studies, Catalogue of Somatic Mutations in Cancer (COSMIC) database, and a study from our group, respectively. *PIK3CA* and *PIK3R1* mutations were identified in 25-52% and 22-28% of endometrial cancers, respectively (28, 53, 54). Interestingly, *PIK3CA* and *PTEN* are frequently mutated simultaneously in endometrial cancers (28, 52). Ovarian cancer is the most lethal gynecological malignancy in the United States and other developed countries. According to the TCGA study, *PIK3CA* is altered in 21% of ovarian cancers. More than 90% of the *PIK3CA* alterations in ovarian cancers are gene amplifications. Alterations in *PTEN* and *PIK3R1* are also identified in ovarian cancers at lower rates (6% and 3%, respectively) (54).

[figure not shown]
[figure not shown]
Proprietary Information of MD Anderson

Protocol 2020-1241

19 October 2022

Activation of PI3K/AKT/mTOR pathway has also been implicated in resistance to endocrine therapies in ER+ breast cancer, indicating that alterations in PI3K/AKT/mTOR pathway might also contribute to resistance in other HR+ gynecological cancers to endocrine therapies (3, 48, 49). Endocrine therapies, including fulvestrant, have been investigated for use in the treatment of gynecological malignancies and have demonstrated modest single-agent clinical activity (9-11). Similar to breast cancer, efficacy is limited by *de novo* and acquired endocrine resistance, and endocrine resistance can be overcome by PI3K pathway inhibition (12-14). Also, our group and others have demonstrated that combinations of mTOR inhibitors with hormone therapy can be effective in gynecological malignancies (14, 15).

PI3K blockade, in combination with hormone therapy, demonstrated clinical activity in different gynecological and breast cancers. Specifically, the Phase 3 SOLAR-1 trial demonstrated the efficacy of the PI3K- α specific inhibitor alpelisib in combination with fulvestrant in the treatment of *PIK3CA*-mutated, hormone receptor HR+ advanced or metastatic breast cancer refractory to hormone regimen (1). Given the findings of the SOLAR-1 trial, we hypothesize that the clinical benefit of the PI3K pathway inhibitors and endocrine therapy combination can be extended to other HR+ solid cancers harboring alterations that activate the PI3K pathway.

Proprietary Information of MD Anderson

Protocol 2020-1241

19 October 2022

2 STUDY OBJECTIVES

The objective of this phase 2 basket study is to evaluate the efficacy and safety of copanlisib in combination with fulvestrant administered to subjects with selected ER+ and/or PR+ advanced or metastatic solid tumors with PI3K and/or PTEN alterations

2.1 Part 1: Dose confirmation:

Primary Objective:

- To evaluate the safety, tolerability, and DLTs of copanlisib 60 mg administered IV on Days 1, 8 and 15 in combination with fulvestrant 500 mg administered IM on Day 1 and Day 15 of Cycle 1, and then on Day 1 of each subsequent 28-day cycle to confirm the RP2D of the combination therapy.

Secondary objectives:

- To assess the efficacy of copanlisib administered in combination with fulvestrant as outlined in Part 2 by evaluating the ORR.
- To evaluate additional efficacy measures such as PFS and OS of copanlisib in combination with fulvestrant.

Exploratory Objective:

- To investigate clonal evolution, and mechanisms of resistance using tissue and liquid biopsies utilizing ctDNA as outlined in Part 2.

2.2 Part 2: Dose expansion:

Primary objective:

- To assess the efficacy of copanlisib administered in combination with fulvestrant as outlined above by evaluating the ORR. Patients enrolled for Part 1 will be included in this efficacy analysis.

Secondary Objectives:

- To evaluate additional efficacy measures such as PFS and OS of copanlisib in combination with fulvestrant.
- To evaluate the safety and tolerability of copanlisib in combination with fulvestrant.

Exploratory Objective:

- To investigate clonal evolution, and mechanisms of resistance using tissue and liquid biopsies utilizing ctDNA.

Proprietary Information of MD Anderson

Protocol 2020-1241

19 October 2022

3 STUDY ENDPOINTS

3.1 Efficacy endpoints:

Radiographic tumor assessments (CT scan or MRI) will be performed by RECIST 1.1. The endpoints of efficacy assessment include:

- ORR described as the proportion of patients who achieve CR or PR by the combination therapy.
- PFS described as the time from study treatment initiation to the date of disease progression or death due to any cause. Patients without progression will be censored at the time of the last follow up.
- OS described as the time from study treatment initiation to the date of death due to any cause. Patients without progression will be censored at the time of the last follow up.

3.2 Safety endpoints:

- Incidence of AEs including but not limited to treatment-emergent AEs, serious AEs, deaths, and clinical laboratory abnormalities, as assessed by the NCI CTCAE v5.0.
- DLT is defined as any of the following adverse reaction observed during first cycle of treatment, and assessed as *possibly*, *probably* or *definitely* related to treatment with copanlisib in combination with fulvestrant. NCI CTCAE v. 5.0 will be used for grading of AEs.

- **Non-hematological AEs:**

- Grade ≥ 2 non-infectious pneumonitis
- Laboratory abnormalities meeting Hy's law criteria (AST or ALT $>3 \times$ ULN with concomitant TB $>2 \times$ ULN). (FDA 2009)
- Any \geq Grade 3 AE, except:
 - Grade 3 fatigue lasting ≤ 5 days
 - Grade 3 nausea or vomiting that has resolved to grade ≤ 2 within 3 days after standard antiemetic therapies
 - Grade 3 diarrhea that has resolved to grade ≤ 2 within 3 days after standard antidiarrheal therapies
 - Isolated laboratory findings not associated with signs or symptoms and lasting less than 3 days, including but not limited to grade 3/4 alkaline phosphatase, uric acid, amylase, and lipase elevations, and grade 3 electrolyte laboratory abnormalities hypophosphatemia, hypokalemia,

Proprietary Information of MD Anderson

Protocol 2020-1241

19 October 2022

hypocalcemia, or hypomagnesemia responsive to supplementation and grade 3/4 lymphopenia.

- Grade 3 hyperglycemia lasting ≤ 7 days

- **Hematological AEs:**

- Grade 4 neutropenia lasting ≥ 7 consecutive days
- Grade 3 and grade 4 febrile neutropenia
- Grade 4 anemia (in the absence of disease progression in bone marrow)
- Grade 3 anemia requiring blood transfusion
- Grade 4 thrombocytopenia of any duration
- Grade 3 thrombocytopenia lasting ≥ 7 consecutive days or associated with bleeding

- **The following event is classified as a DLT:**

- If a full cycle of copanlisib (3 doses) will not be completed due to any study intervention-related AE, the AE is considered as a DLT
- A delay of over 1 week in initiating Cycle 2 of copanlisib and/or fulvestrant treatment occurs secondary to any study drug related AE, the AE will be considered a DLT
- Death not clearly attributed to underlying disease or alternative cause

Note: Allergic reactions leading to discontinuation of study interventions will not be considered as a DLT and participant will be replaced.

3.3 Exploratory endpoints:

Biomarker-based studies will be performed using tumor tissue and liquid biopsies to assess clonal evolution, and mechanisms of innate and adaptive resistance.

Tumor biopsies, if medically feasible, will be obtained at screening (within 28 days of Cycle 1, Day 1) on-treatment after fulvestrant and copanlisib administration on Cycle 2 Day 1 and at EOT. Biopsies will be optional but encouraged, especially in patients with a response or prolonged disease control. Examples of studies include identification of genomic biomarkers of response and intrinsic or adaptive resistance by whole exome, targeted NGS, and Nanostring DSP or other similar methods.

Proprietary Information of MD Anderson

Protocol 2020-1241

19 October 2022

[figure not shown]
Mandatory blood samples to isolate plasma ctDNA will be collected at pre-treatment (Day -28 to Day1 of Cycle 1), on-treatment (pre-dose -at the same time as the on treatment biopsy- on Cycle 2 Day 1 as well as at the first two restaging visits), and post-treatment at EoT.

Plasma ctDNA samples will be used to evaluate changes in ctDNA quantity and clonal evolution by selected molecular methods that may include targeted NGS, methylation sequencing, and droplet digital polymerase chain reaction.

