4 INVESTIGATIONAL PLAN

4.1 Study Design

We propose to conduct a multi-arm, open-label, phase 2 basket trial investigating the efficacy and safety of copanlisib in combination with fulvestrant in patients with selected HR+ advanced or metastatic solid cancers, harboring PI3K or PTEN alterations including ovarian cancer (cohort 1), endometrial cancer (cohort 2), and breast cancer (cohort 3). Cohort 3 will be enriched to include at least 7 patients naïve to any PI3Ki in Stage 1 and also in Stage 2.

Proprietary Information of MD Anderson

Protocol 2020-1241

19 October 2022

and will be contacted by telephone every 12 weeks (± 14 days) for survival status until death, withdrawal of consent, or lost to follow-up.

Exploratory biomarker studies using pre-treatment, on-treatment, and post-progression tumor biopsy tissues and serially collected blood liquid biopsies will investigate clonal evolution, and mechanisms of innate and adaptive resistance.

The study will consist of a screening/baseline phase, treatment phase, safety follow-up, follow-up visits, and survival follow-up.

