4.1.5 Survival Follow-Up

Patients who experience confirmed disease progression or initiate a new anticancer therapy will move into the survival follow-up phase. Patients will be contacted by telephone every 12 weeks (± 14 days) for survival status until death, withdrawal of consent, or lost to follow-up.

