or lost to follow-up. After confirmed disease progression, each patient will be followed for survival status until death, withdrawal of consent, or lost to follow-up.

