8.2 Efficacy Analysis

The ORR is defined as the proportion of patients who achieve CR or PR by the combination therapy per RECIST 1.1. Bayesian beta-binomial model and the CBHM will be used to model the data observed within each cohort. Bayesian 95% credible interval will be derived. Summary statistics will be given for secondary efficacy endpoints without borrowing information across cohorts. Time-to-event methodology will be used to assess mortality outcomes. Specifically, a log-rank statistic (accompanied by a Kaplan-Meier plot) will be the primary method of analysis for the mortality endpoint. Model-based methods (e.g., Cox proportional hazards or other robust methods) may also be applied.

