For equivocal findings of progression (e.g., very small and uncertain new lesions; cystic changes or necrosis in existing lesions), treatment may continue until the next scheduled assessment. If at the next scheduled assessment, progression is confirmed, the date of progression should be the earlier date when

Proprietary Information of MD Anderson

Protocol 2020-1241

19 October 2022

progression was suspected.

Stable Disease (SD): Neither sufficient shrinkage to qualify for PR, nor sufficient increase to qualify for PD, taking as reference the smallest sum diameters while on study.

Not Evaluable (NE): When an incomplete radiographical assessment of target lesions is performed or there is a change in the method of measurement from baseline that impacts the ability to make a reliable evaluation of response.

Evaluation of Non-Target Lesions

Complete Response: Disappearance of all non-target lesions and normalization of tumor marker level. All lymph nodes must be non-pathological or normal in size (<10 mm short axis).

Non-CR/Non-PD: Persistence of 1 or more non-target lesions and/or maintenance of tumor marker level above the normal limits.

PD: Unequivocal progression of existing non-target lesions. The appearance of 1 or more new lesions is also considered progression.

NE: When a change in method of measurement from baseline occurs and impacts the ability to make a reliable evaluation of response.

Evaluation of Best Overall Response

The best overall response (BOR) is the best response recorded from the start of the study treatment until the earliest of objective progression or initiation of new anticancer therapy, taking into account any requirement for confirmation. The patient's BOR assignment will depend on the findings of both target and non-target disease and will also take into consideration the appearance of new lesions. The BOR will be calculated via an algorithm using the assessment responses provided by the investigator over the course of the study.

Time Point Response

It is assumed that at each protocol-specified time point, a response assessment occurs. (When no imaging/measurement is conducted/made at all at a particular time point, the patient is NE at that time point.) **Table 21** provides a summary of the overall response status calculation at each time point for patients who have measurable disease at baseline.

Table 21: Time Point Response: Patients with Target (\pm Non-target) Disease

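### The OS definition ends with the PFS censoring sentence: read literally, a death without progression is both event and censored, and patients alive after progression have no visible censoring rule

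*Combined protocol and SAP*

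**What the plan says.** The OS bullet in Section 3.1 starts the clock at first study treatment. Its event and censoring rule reads: "date of death due to any cause. Patients without progression will be censored at the time of the last follow up". The PFS bullet directly above it closes with the same sentence: "date of disease progression or death due to any cause. Patients without progression will be censored at the time of the last follow up". The Study endpoints row of the synopsis repeats both bullets unchanged, so neither place corrects the other.

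Section 2 lists both endpoints as secondary objectives in Part 1 and in Part 2: "To evaluate additional efficacy measures such as PFS and OS of copanlisib in combination with fulvestrant".

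The protocol plans to learn the vital status of patients after progression. Section 4.1.5 states: "Patients who experience confirmed disease progression or initiate a new anticancer therapy will move into the survival follow-up phase". Section 6.9 states: "After confirmed disease progression, each patient will be followed for survival status until death, withdrawal of consent, or lost to follow-up". Section 4.1 and footnote w of Appendix A describe 12-weekly telephone contact "for survival status until death, withdrawal of consent, or lost to follow-up".

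For the analysis, Section 8.2 says that "a log-rank statistic (accompanied by a Kaplan-Meier plot) will be the primary method of analysis for the mortality endpoint", and allows model-based methods in addition. Its visible text gives no censoring rule for OS or PFS. The opening of Section 8 is not shown.

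**The concern.** A censoring rule for OS has to turn on whether the patient is known to have died. This one turns on progression. The sentence fits PFS, apart from one missing reference to death, and appears to have been carried down into the OS bullet.

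The Kaplan-Meier curve and any log-rank test rest on one event-or-censored flag and one date per patient. If the definition gives two answers for some patients and none for others, two analysts following the protocol can produce different OS results from the same data. The choice between them would then be made at analysis, with outcomes already known in an open-label trial.

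**Working it through.** No figure in the plan needs reproducing, so the check applies the written rules to every possible patient state.

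**OS as written**

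| State at analysis | Event sentence | Censoring sentence, read literally | Result |
|---|---|---|---|
| Dead, progressed | event | does not apply | event |
| Dead, no documented progression | event | censored | contradiction |
| Alive, no progression | no event | censored | censored |
| Alive, progressed | no event | does not apply | no rule |

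Two of the four states fail.

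The protocol itself can produce both failing states. Section 4.1.5 moves patients into telephone survival follow-up when they start new anticancer therapy, even without progression. Section 4.1.4 stops tumour imaging at the same point. A later death in such a patient is a death without documented progression. Patients alive after progression are the main group that Sections 4.1.5 and 6.9 keep under survival follow-up.

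**PFS as written**

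| State at analysis | Event sentence | Censoring sentence, read literally | Result |
|---|---|---|---|
| Progressed, alive or dead | event at progression | does not apply | event |
| Dead, no progression | event | censored | contradiction |
| Alive, no progression | no event | censored | censored |

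One of the three states fails. It would not fail if the sentence referred to patients with neither progression nor death.

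**Direction of the effect**

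The Kaplan-Meier estimate is S(t) = product over event times up to t of (1 − d/n), where d is the number of events at that time and n the number at risk. Suppose one death is recoded as censored on its own date. Then d falls by 1, n is unchanged, and that factor rises from 1 − d/n to 1 − (d − 1)/n, a gain of 1/n. No other factor changes, so the curve is higher from that date on. If the censoring date is an earlier contact, the patient leaves the intervening risk sets and the curve is slightly lower over that interval, but it is not lower from the date of death onward. Censoring deaths without progression therefore pushes OS and PFS upward, and by more as such deaths become more common.

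**Size of the effect**

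A figure would need the share of first events that are deaths, the rates of progression and of death after progression, and the follow-up distribution. The documents give none of these. Any figure in months would be chosen by its assumptions, so none is given.

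**After correction**

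Suppose OS is censored only for patients not known to have died, at the date last known alive. Both dead states become events and both alive states become censored, so each of the four has exactly one outcome. Suppose PFS is censored only for patients with neither progression nor death. Each of its three states then also has exactly one outcome.

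**The case against.** The strongest reply is that no competent analyst would apply the sentence literally. The OS event is death from any cause, and the PFS definition names death as an event. The censoring sentence can be read as shorthand for patients who have not yet had the event. Survival follow-up after progression shows that the sponsor means to count those deaths and to censor survivors at last contact. This is largely right: the intent can be inferred, and that makes the remedy a wording change. It does not remove the problem. The shorthand reading asks the analyst to set aside the sentence's own condition. The gap for patients alive after progression also does not depend on strict reading, because the sentence does not cover them.

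A second reply is that the opening of Section 8 is not shown and could hold a proper censoring rule. That stands as a limit: the claim can only be that no rule is visible. Even if one exists there, the endpoint definitions in Section 3.1 and the synopsis would conflict with it and still need correcting.

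A reader might also infer two further faults. One is that the log-rank comparison has no defined groups; these may be named in the part of Section 8 that is not shown. The other is that PFS lacks a cut-off at new anticancer therapy, which Appendix B sets for best response: "the best response recorded from the start of the study treatment until the earliest of objective progression or initiation of new anticancer therapy". Sections 4.1.4 and 6.9 already stop disease follow-up at new therapy, and whether PFS should be censored there is a choice of estimand. The documents do not establish either as an error.

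**Conclusion.** Wrong as written, in both Section 3.1 and the synopsis. The OS censoring sentence contradicts the OS event for deaths without documented progression and leaves patients alive after progression without a visible rule. The PFS sentence contradicts the PFS event for deaths without progression.

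If those deaths were censored as the text says, OS and PFS would be biased upward. Only the direction can be supported.

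A reader might infer that the sponsor plans to censor these deaths, or to leave living progressed patients out of the analysis. The documents do not support that: the event definitions and the survival follow-up point the other way. A reader might also infer that the trial's main conclusions are at risk. They are not, because OS and PFS are secondary and the response-rate and dose-limiting-toxicity conclusions do not use this rule.

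The verdict rests on the visible text, with the opening of Section 8 unseen.

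**What to change.** In Section 3.1 and in the Study endpoints row of the synopsis, replace the closing sentence of each bullet:

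- OS: *Patients not known to have died are censored at the date last known alive, regardless of progression.*
- PFS: *Patients with neither progression nor death are censored at the last evaluable tumour assessment, or at treatment start if there is none.*

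The PFS sentence also ties censoring to a date on which disease status was known, in keeping with the imaging-based definition in Section 3.1. If the part of Section 8 that is not shown contains a censoring rule, align it with these sentences.

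The cost is wording only. Vital status after progression and tumour assessments are already collected. Sample size, visit schedule and primary analysis do not change. The correction should be made before the OS and PFS analyses are run.
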